21. Trial insurance	15
22. Appendix.....	15
22.1. Definitions	15
22.1.1. WHO performance status scale.....	15
22.1.2. Fleischner's society criteria	16
22.2. Technical Procedures.....	16
22.2.1. Procedure for the pathological review of diagnosis.....	16
22.2.2. Procedures for DTS examination.....	16
22.2.3. Quality of Life evaluation.....	17
22.3. References	19
23. Writing Committee and Scientific support:.....	21

Abbreviations

DTS	Digital Tomosynthesis
CT	Computer Tomography
REID	Risk of Exposure-Induced Death
BEIR	Biologic Effects of Ionizing Radiation
QoL	Quality of Life
OS	Overall Survival
LLE	Loss of Life Expectancy
ROC	Receiver Operating Characteristic
NELSON	The Dutch-Belgian Randomized Lung Cancer Screening Trial (Dutch acronym)
ICH	International Conference On Harmonisation
ECOG	Eastern Cooperative Oncology Group
EORTC	European Organisation for Research and Treatment of Cancer
CRF	Case Record Forms

Synopsis

Sponsor	Santa Croce e Carle Hospital founded by the Fondazione CRC di Cuneo
Project Title	A monocenter prospective no-profit interventional study for lung cancer early diagnosis with tomosynthesis: re-evaluation of lung nodule detection rate at 5 years
Version	July 15 th , 2017
Study Phases	Phase 3
Coordinators	[name] (study chairman), [name] (study coordinator)
Statistician	[name] (University of Torino)
Writing Committee	[name] (Nuclear Medicine Division), [name], [name] (Anatomical Pathology Division), [name], [name] (Medical Phisics Division), [name] (Oncology Division), [name] (Radiology Division), [name], [name], [name] (Thoracic Surgery Division), [name] (Pneumology Division), [name] (Health Management), [name] (Radiotherapy Division).
Population	Subjects enrolled in previously closed SOS trial (high risk subjects for lung cancer) without confirmed lung cancer.
Study Objectives	To evaluate the lung cancer detection rate in the population of high risks subjects previously enrolled in lung cancer screening trial with chest digital tomosynthesis (SOS trial).
Participating centers	Single center, Santa Croce e Carle Hospital
Overall Study design	
The study aims to evaluate the lung cancer detection rate. Patients that previously were enrolled in SOS study will be called by project assistants and booked for DTS examination. In case the subject refuses to perform examination a phone interview for follow-up will be carried out acquiring information on the status of the subject, on the variation of quality of life, on smoke habits and on attitude toward lung cancer screening.
 
For the subject accepting the DTS examination the same questionnaire will be filled onsite just before examination. DTS will be then performed and blindly evaluated by two radiologists. DTS findings will be classified based on their dimension (large axis measurement), radiological characteristics (calcific, pleural, solid, partially solid and ground glass opacity) and position (in the 5 lobes). Findings will be then classified using LUNG-RADS [1]. The results of the DTS,in case of negative report, will be communicated with a letter to the patient.
 
The subjects with one or more nodules larger than 5 mm, not clearly benign, will undergo diagnostic contrast enhanced CT and will be followed according to Fleischner society [2] criteria.

	Discordant and positive cases will be discussed in a consensus session among radiologists and thoracic surgeons. The consensus results will be used in the following analysis.
Endpoints	
Primary
 
Lung cancer detection rate.
 
Secondary
 
 • Percentage of lung cancer addressed to radical surgery treatment; • Sensitivity of DTS evaluating the number of lung cancer occurred in the population of SOS study in the last 5 years; • Mortality • Overall survival (OS) • Quality of Life (QoL) • Cost-effectiveness
Eligibility criteria	
Inclusion criteria:
 
 • current or former smoker status; • for former smokers, the maximum time since quitting smoking must be below 10 years. • smoking history of at least 20 pack-years; • age 45-80 years; • no previous history of cancer in the 10 years before the beginning of the study; • be able to stand and hold the breath for 11 seconds during image acquisition • previous participation to SOS trial 
Exclusion criteria:
 
 • pregnancy
DTS	
Acquisition
 
DTS is performed with Discovery XR650 (GE Healthcare, Milwaukee, WI). Images are acquired with a source-to-image distance of 180 cm. The tube voltage is set to 120 kVp with 3 mm Al inherent and 0.2 mm additional Cu filtration. The DTS acquisition consists of 60 projection images along a vertical source path spanning 30° of total tube angular motion. The set of 60 images is acquired in 10 s in breath hold condition. Images are reconstructed at 3 mm plane spacing in the coronal plane. Image reconstruction is done using a filtered back-projection algorithm and a sliding average of seven adjacent planes is taken to reduce noise and low-contrast tomosynthesis artifacts.
 
Dose
 
The mean effective dose expected for DTS is 0.09 ± 0.04 mSv. Based on organ doses the loss of life expectancy (LLE) and the risk of exposure-induced death (REID) are calculated for lung cancer for man and women and for breast cancer for women using BEIRVII[3] model. REID for lung cancer for men and women are 10/100.000 and 3/100.000 respectively. REID for breast cancer for women are 10/100.000. LLE were 0.2 h for men and 0.6 h for women. These values are small respect to the baseline mortality in the normal population that are 7700/100.000 and 4.600/100.000 for lung cancer for men and women and 3.000/100.000 for breast cancer [3].
 
Referral

	Two independent radiologists carry out blinded independent central reviewing for DTS. Discordant and positive cases are discussed in consensus.
Treatment	Subjects are managed in line with Fleischchner Society criteria for the management of small pulmonary nodules and treated using physicians' choice (no indication is given to treatment of patient from this trial).
Radiotherapy	Radiotherapy is performed based on physician's choice (no indication is given to treatment of patient from this trial).
Sample size	
The primary objective of this study is to calculate the detection rate on lung cancer at 5 years distance from the previous DTS. In the SOS study 1843 subjects were enrolled and lung cancer was found in 18 (0.8%) of them at baseline. 1703 subjects performed the first round DTS at one-year distance and lung cancer was found in 5 (0.3%) of them.
 
The number of patients needed to be confident that the disease will be detected if present at or above the specified prevalence of 0.3% with a confidence of 5% (i.e. assuming that the true prevalence is at least 0.3%, then a sample consisting only of subjects without lung cancer would occur 5% of the time or less given a sample with the calculated size) is 998. Allowing for a drop out of no more than 50%, a minimum number of 1496 subjects is required.

Timelines	
Expected accrual time: September 2017 / August 2018
 
Patients with positive TC will be subjected to diagnostic investigations to identify the pathology according to Fleischner Society. Length of Follow-up: no follow-up is foreseen for these patients

Background and rationale	
Lung cancer is the leading cause of cancer-related death around the world. In 2008 there were nearly 1.6 million new cases worldwide, accounting for the 12.7% of all new cancer diagnoses[4]. Despite decreasing trends in smoking and resulting decrease in lung cancer mortality, the population at risk for lung cancer continues to be large[5]. In the past years several programs have been developed to screen for lung cancer using low-dose chest computed radiography (CT). However, only recently different studies demonstrated a clear reduction in mortality[5,6]. In particular, NLST low dose CT screening trial demonstrated a 6.7% reduction in the death rate compared to chest X-ray with a positive screening test rate for lung cancer detection of 24.2%, compared to 6.9% for conventional X-ray[7]. The use of CT as a screening test has nonetheless recently prevailed over the concern for the cost and the radiation burden[8]. Digital tomosynthesis (DTS) is a limited angle tomography that allows reconstruction of multiple image planes from a set of projection data acquired over a relatively small angle of X-ray tube movement[9]. Santa Croce and Carle Hospital has this technology from March 2010, thanks to a donation of Fondazione CRC. Although it does not have the spatial depth resolution of computed tomography, it provides high-resolution images in the sagittal planes at a lower dose and cost than CT[10]. Several studies have shown that DTS offers advantages over conventional chest X-ray and comparable of those of CT[11–13]. The Studio OSservazionale (SOS) was a clinical trial conducted within Santa Croce e Carle Hospital sponsored by Fondazione CRC analysing smokers and former smokers aged 45–80 with no cancer diagnosis. All the subjects in whom a suspicious nodule was detected by DTS underwent diagnostic CT. The SOS study demonstrated that baseline DTS detected pulmonary abnormalities in 14.5% and lung cancer in 1.0% of the subjects[14], comparable to results obtained in CT screening programs. A second DTS, within the same study, executed one year later reported pulmonary abnormalities in 0.7% and lung cancer in 0.3% of the subjects[15].

1. Background and introduction

Lung cancer is the leading cause of cancer-related death around the world, it represents 13% of all new cancer diagnoses [4]. The lung cancer incidence is gradually increasing, especially among women and young people, but the fraction of cured patient remains low. In 80% of cases lung cancer, in early phase, is treatable only with surgery without chemotherapy or adjuvant radiotherapy and the survival perspective at five years exceeds 70% [4]. Recently several studies [5,16] showed a relative reduction in lung cancer mortality of 20% in high-risk subjects enrolled in screening trials performed with low-dose Chest CT [7]. As a consequence, several of scientific guidelines recommended chest Computed Tomography (CT) in lung cancer screening. CT examination allows detection of small nodules and a good quality of the image but its disadvantages includes high cost and high radiation dose [8]. Digital tomosynthesis (DTS) is a limited angle tomography that allows reconstruction of coronal images from a set of projection acquired over a small angle of X-ray tube movement [9]. This technique is available in the AO Santa Croce e Carle since 2010 and more than 5000 have been executed with it. Several studies demonstrates that DTS is a reasonable alternative to the CT and allows a better evaluation of suspects nodules compared to conventional chest RX [11-13].

2. Objectives of the trial

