3.2. Exclusion criteria

[figure not shown]
Exclusion criteria:

- pregnancy

4. Trial Design

During this study, about 1700 subjects, who have been enrolled in SOS Observational Study will undergo a DTS. The study will be presented as an observational clinical trial and registered on clinicaltrials.gov. Initially, all the subjects that participated in the SOS study, will be contacted by phone and invited to perform a DTS in Carle Hospital. When accessing the hospital the subjects will be asked to fill-in a form to confirm that the inclusion criteria of the SOS study are still met. DTS will be then performed and blindly evaluated by two radiologists. DTS findings will be classified based on their dimension (large axis measurement), radiological characteristics (calcific, pleural, solid, partially solid and ground glass opacity) and position (in the 5 lobes). Findings will be then classified using LUNG-RADS[1] schema and ROC analysis will be applied. Inter-observer variability will be analyzed with Krippendorff's Alpha[17].

Discordant and positive cases will be discussed in a consensus session among radiologists and thoracic surgeons. The consensus results will be used in the following analysis. The subjects with one or more nodules larger than 5 mm, not clearly benign, will undergo diagnostic contrast enhanced CT and will be followed in line with Fleischner Society[2].

5. Evaluation criteria

Lung cancer will be histologically proven, following the procedure of Pathology Division that use a double blinded analysis of biological material.

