5.1. Overall survival

Overall survival (OS) defined as the time from randomization until death as a result of any cause (with at least five years of follow-up).

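### The synopsis foresees no follow-up for CT-positive patients, against the design text and the overall survival definition, and no rule says whether a cancer proven after the first work-up counts in the primary detection rate

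*Combined protocol and SAP*

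**What the plan says.** Statements on follow-up stand in several places in the combined protocol and SAP.

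- **Synopsis, Timelines.** "Patients with positive TC will be subjected to diagnostic investigations to identify the pathology according to Fleischner Society". The next sentence reads "Length of Follow-up: no follow-up is foreseen for these patients". I read TC as CT.
- **Synopsis, Overall Study design.** Subjects with a nodule above 5 mm that is not plainly benign "will undergo diagnostic contrast enhanced CT and will be followed according to Fleischner society [2] criteria".
- **Section 4, Trial Design.** The same subjects "will undergo diagnostic contrast enhanced CT and will be followed in line with Fleischner Society".
- **Synopsis, Treatment.** "Subjects are managed in line with Fleischchner Society criteria for the management of small pulmonary nodules"; treatment itself is left to the physician.
- **Section 5.1.** Overall survival, a secondary endpoint, is the "time from randomization until death as a result of any cause (with at least five years of follow-up".
- **Section 22.2.4.** The logistics checklist lists a follow-up eCRF without saying for whom or when.

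The primary endpoint is the lung cancer detection rate, and Section 5 requires histological proof. No section says how long after the recall DTS a proven cancer still counts. The end-of-study criteria in Section 6.3 do not require that diagnostic work-up be complete.

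**The concern.** The Timelines row and the two design statements do not fit together as written. One foresees no follow-up for CT-positive patients; the others say that a group containing those patients will be followed.

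This reaches the primary endpoint because cancer must be proven by histology, and proof can come after the first CT. The table printed in Section 22.1.2 (a Lung-RADS table under a Fleischner heading) pairs category 3 with a repeat CT at 6 months and category 4A with one at 3 months. If a nodule is indeterminate at first work-up and proven malignant later, the design text suggests that the study would learn of it. The Timelines row, taken literally, suggests that it might not. This concerns subjects examined on the first day as much as those examined on the last. With so few cancers expected, each one matters.

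Overall survival is also exposed: a definition that needs at least five years of follow-up cannot be met, for time counted from entry to this study, in patients who have none.

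**Working it through.** **1. The statements side by side**

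| Place | Group | Follow-up |
|---|---|---|
| Synopsis, Timelines | CT-positive | none foreseen, after Fleischner-guided investigation |
| Synopsis, Overall Study design | all sent to CT | yes, Fleischner |
| Section 4 | all sent to CT | yes, Fleischner |
| Section 5.1 | not restricted | at least five years |
| Section 22.2.4 | not stated | a form is listed |

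The CT-positive patients are a subset of those sent to CT, so the first three rows overlap for them. The form in the last row is weak evidence. It could serve the telephone interview of subjects who decline DTS, or the mortality endpoint.

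**2. The plan's own figure**

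Inputs from Section 6.1.1: rate p = 0.003; probability of zero cases at most 0.05.

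n = ln(0.05) / ln(1 − 0.003) = 997.08, rounded up to 998, which matches the plan. At n = 998, P(zero cases) = 0.997^998 = 0.0499.

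**3. Weight of one case**

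- 998 subjects: 998 × 0.003 = 2.99 expected cancers, so one case is about a third.
- 1496 subjects, if all were examined: 1496 × 0.003 = 4.49, so one case is about 22%.
- About 1700 subjects (Section 4): 5.1, so one case is about 20%.

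For scale, 3/998 is 0.30% (exact 95% interval 0.06% to 0.88%) and 2/998 is 0.20% (0.02% to 0.72%). One case is a large share of the estimate but lies well inside its sampling error.

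**4. If a share f of cancers went uncounted**

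The documents do not give f, so the values are assumptions. Counted rate = 0.003 × (1 − f); P(zero) = (1 − counted rate)^998; required n = ln(0.05) / ln(1 − counted rate).

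| f | Counted rate | P(zero) at 998 | Required n |
|---|---|---|---|
| 0% | 0.30% | 5.0% | 998 |
| 20% | 0.24% | 9.1% | 1247 |
| 40% | 0.18% | 16.6% | 1663 |

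**5. Timeline**

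Section 6.4 plans the start for September 2017 and the last entry for the end of August 2018. Section 6.3 allows the study to end one year after start-up if its other two criteria are also met. At the earliest closure, the last entrants would have roughly 0 to 1 month of observation, against repeat-imaging intervals of 3 and 6 months in the appendix table.

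**The case against.** The best defence is that the Timelines row should be read as a whole. Its preceding sentence keeps Fleischner-guided investigation aimed at identifying the pathology, and the Treatment row keeps Fleischner management. The row may then mean work-up until the pathology is known and no study follow-up after that, which is compatible with the design text. That reading is reasonable, but the protocol does not state it, and it still conflicts with the five years in Section 5.1. That conflict would soften if survival were counted from SOS enrolment. However, Section 5.1 starts the clock at randomization in a study that describes no randomised comparison, so the origin is not settled either.

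Several stronger inferences are tempting and are not supported:

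- **That CT-positive patients lose care, or that staff receive flatly opposite orders.** Two synopsis rows keep Fleischner-guided management or investigation. What is shown is an ambiguity.
- **That late-proven cancers are excluded.** No section says so. Exclusion is a possible result of the literal reading combined with the missing time window.
- **That the detection rate falls by a third.** That is the effect of one omitted case at 998 subjects, and the number omitted is unknown.
- **That the repeat-imaging intervals show late proof will be common.** The protocol uses Lung-RADS to classify findings and names Fleischner for follow-up. The Fleischner intervals are not printed.

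It is also fair to say that rewording the Timelines row alone would not settle which cancers count. The missing ascertainment window has to be filled as well.

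**Conclusion.** The inconsistency is real and stands in the current text. The Timelines row conflicts with the synopsis design row and Section 4 unless a qualification is added that the protocol does not contain, and it conflicts with Section 5.1 as written. The follow-up eCRF adds little.

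The consequence for the primary endpoint is conditional. If the Timelines row is applied literally, cancers proven only after the first work-up may go uncounted and the detection rate would be biased downwards. If it means only that study follow-up stops after a completed work-up, the bias may be small or absent, but the status of later-proven cancers remains undefined. The figures for 20% and 40% uncounted show sensitivity, not an estimate. They rest on the plan's 0.3%, on 998 examined subjects, and on assumed shares. They do show that the plan's single sample-size criterion, at most a 5% chance of seeing no case, has almost no slack: it is 4.99% with every cancer counted.

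This should be corrected before analysis. It does not show that care is withheld or that the design is unsound.

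**What to change.** 1. Reconcile the synopsis (Timelines and Overall Study design), Section 4, Section 5.1 and the checklist in Section 22.2.4, so that one statement on follow-up applies throughout. Which clinical rule is right is for the investigators. Say which subjects the follow-up eCRF is for.
2. In the primary endpoint definition, state that a cancer histologically proven in a nodule first reported at the recall DTS counts whether it is proven at first work-up or later, up to one stated ascertainment cut-off that is the same for all subjects. Record the date of proof.
3. Align the end-of-study criteria in Section 6.3, and the timeline in Section 6.4 where needed, with that cut-off.

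The cost is an amendment touching these sections, plus a somewhat later final status and database lock on account of a few subjects. A form that could hold the date of proof is already listed.

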2.1. General objectives

To evaluate the lung cancer detection rate in the population of high risks subjects previously enrolled in lung cancer screening trial with chest digital tomosynthesis (SOS trial).

Repeating the DTS at 5 years from the baseline exam will permit to pursue three different tasks:

- 1) find subjects with lung cancer to be addressed to radical surgery treatment;
- 2) calculate the sensitivity of DTS evaluating the number of lung cancer occurred in the population of SOS study in the last 5 years;
- 3) establish the correct timing for DTS screening.

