3.1. Patients inclusion criteria

Inclusion criteria:

- current or former smoker status;
- for former smokers, the maximum time since quitting smoking below 10 years.
- smoking history of at least 20 pack-years;
- age 45-75 years;

- no previous history of cancer in the 10 years before the start of the study;
- be able to stand and hold the breath for 11 seconds during image acquisition
- previous participation to SOS trial

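### DTS sensitivity counts every lung cancer of the last 5 years with no interval defining a miss, and the 5-year DTS has no reference standard in negatives

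*Combined protocol and SAP*

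**What the plan says.** The Synopsis lists DTS sensitivity as a secondary endpoint, and section 2.1 makes it one of three tasks: to "calculate the sensitivity of DTS evaluating the number of lung cancer occurred in the population of SOS study in the last 5 years". The endpoint list in section 2.2 omits it. Section 6.2 contains only Lung-RADS classification, an ROC analysis and Krippendorff's alpha. It gives no numerator, denominator, rule for a missed cancer or confidence interval for sensitivity.

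The 5 years have two starting points: the baseline examination in section 2.1 and the previous DTS in section 6.1.1.

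The Synopsis defines the study population as "Subjects enrolled in previously closed SOS trial (high risk subjects for lung cancer) without confirmed lung cancer", and section 3.1 requires "no previous history of cancer in the 10 years before the start of the study". For case finding, section 4 says that "all the subjects that participated in the SOS study, will be contacted by phone and invited to perform a DTS". For a subject who refuses the examination, the Synopsis says that "a phone interview for follow-up will be carried out acquiring information on the status of the subject". It adds: "For the subject accepting the DTS examination the same questionnaire will be filled onsite just before examination". Section 6.3 allows closure once at least 80% of SOS subjects have been contacted, together with two other conditions.

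For the new DTS, section 4 states: "The subjects with one or more nodules larger than 5 mm, not clearly benign, will undergo diagnostic contrast enhanced CT". Section 5 requires histological proof of lung cancer. The Synopsis provides a letter for a negative report.

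**The concern.** Sensitivity is the share of cancers present at the examination that the examination found. A cancer diagnosed four years after a negative DTS may not have existed at that DTS. If it counts as a miss, the result reflects the length of the look-back as well as the performance of the test. The plan gives a counting period but no such interval, so the analyst must choose one, possibly after seeing the data.

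Three further gaps bear on the same figure.

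- **First-round cancers.** The plan does not say whether the 5 cancers found at the first SOS round are also misses of the baseline DTS.
- **Ascertainment.** The missed cancers lie among SOS subjects diagnosed since a negative DTS, who cannot enter the new study. The status interview is described only for refusers and attenders. No source of cancer status is named for ineligible or deceased subjects. Cancers not found make sensitivity look too high.
- **The new DTS.** With CT and histology only in positives, a cancer missed by the consensus reading is not observed.

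At stake is a named secondary endpoint and the information it would give on screening timing, which is another of the three tasks.

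**Working it through.** **Inputs.** Section 6.1.1 gives 18 cancers among 1843 subjects at baseline, 5 among 1703 at the first round one year later, and an annual incidence of 0.3%. The plan states no sensitivity figure to reproduce. The 0.3% does reproduce: 5/1703 = 0.29%. So does the sample size built on it: ln(0.05)/ln(1 − 0.003) = 997.08, rounded up to 998. I use the count of 18, because 18/1843 is 0.98% and not the printed 0.8%.

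**Assumptions.** Detected D = 18 + 5 = 23. At risk after the first round N = 1703 − 5 = 1698. Incidence i is constant at 0.3% per year, and all later cancers are found and counted as misses.

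**Effect of the interval.** Later cancers M = N × [1 − (1 − i)^t]; sensitivity = D/(D + M). Because the first round came one year after baseline, t = 4 matches 5 years from baseline (section 2.1). Taking the first round as the previous DTS, t = 5 matches section 6.1.1.

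| Interval t | M | Sensitivity | Whole numbers, exact 95% CI |
|---|---|---|---|
| 1 year | 5.1 | 81.9% | 23/28, 63 to 94% |
| 4 years | 20.3 | 53.1% | 23/43, 38 to 69% |
| 5 years | 25.3 | 47.6% | 23/48, 33 to 63% |

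**Range of i.** At 0.2% per year the three figures are 87%, 63% and 58%. At 0.5% they are 73%, 41% and 35%.

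**Choice of N.** Applying the rate to all 1843 gives 1843 × 0.003 = 5.5 cancers in 1 year and 22.1 in 4 years. Sensitivity is then 23/28.5 = 81% and 23/45.1 = 51%. The conclusion does not depend on this choice, but 1698 is the group at risk after round 1.

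**First-round cancers.** Baseline sensitivity is 18/18 = 100% if none of the 5 is a baseline miss, and 18/23 = 78% (56 to 93%) if all are.

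**Incomplete ascertainment.** If 20% of subjects are not contacted and have the same rate, M falls to 0.8M.

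| Interval | All found | 80% found | Difference |
|---|---|---|---|
| 1 year | 81.9% | 84.9% | about 3 points |
| 4 years | 53.1% | 58.6% | 5.5 points |
| 5 years | 47.6% | 53.2% | 5.6 points |

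**The 5-year DTS.** Sensitivity = TP/(TP + FN). Without CT, histology or cancer follow-up in DTS-negatives, no FN of the consensus reading can be observed. The ratio is then TP/TP = 100%, whatever the true value. Section 5.1 does not help, since it follows subjects only "until death as a result of any cause (with at least five years of follow-up". The checklist in 22.2.4 names a follow-up form without content. The Synopsis remark that no follow-up is foreseen concerns CT-positive patients and sits awkwardly with section 5.1, but neither text provides cancer follow-up of negatives.

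**The case against.** The strongest reply is that the plan does state a rule: every cancer of the last 5 years counts. Late cancers are also relevant to screening timing, and 12 months is only one convention. This is fair as far as it goes. The plan is not silent, and late cancers should be reported. But a rule that counts them as misses measures something other than sensitivity, and the two texts disagree on when the 5 years begin.

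A reader might infer that subjects with an interval cancer are lost from the count. The documents do not support that. The endpoint refers to the SOS population, everyone in it is to be phoned, the mortality endpoints imply that vital status will be obtained, and section 18.3 foresees review of medical records. What is missing is a stated source of lung-cancer status for ineligible and deceased subjects. Nor is the 80% a planned loss of 20%. It is a minimum for closing, so the 3 to 6 points are a worst case for non-contact at the assumed rate.

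A reader might also infer that the ROC analysis has no reference at all. That goes too far. With two blinded readers, a reader-level ROC against the consensus or against CT-verified results is possible, and one reader can miss what the other finds. The gap concerns patient-level ROC and consensus-read sensitivity.

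Finally, 0.3% is a first-round screening yield, called a prevalence in the Synopsis and an annual incidence in section 6.1.1. It is not a measured rate of interval cancers, so the percentages above are illustrations.

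**Conclusion.** The point holds for a secondary endpoint and should be fixed. Followed literally, the counting rule mixes missed cancers with later ones. Taken alone, it understates sensitivity: about 53% or 48% instead of about 82%, given 23 detected cancers, 1698 at risk, a constant 0.3% per year and complete case finding. Separately, the treatment of the 5 first-round cancers moves baseline sensitivity between 100% and 78%. Partial ascertainment acts in the opposite direction. It is therefore tempting to say that the reported figure will be too low, or too high, but the documents do not fix the net direction. For the 5-year DTS, the consensus reading has no observable false negatives, so a patient-level sensitivity would carry no information. The primary endpoint, the detection rate, is unaffected.

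**What to change.** (a) State that the endpoint is the sensitivity of the SOS rounds, reported by round, in the SOS subjects who had a DTS in that round, regardless of eligibility for the new DTS. Reconcile the start of the 5 years between sections 2.1 and 6.1.1.

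(b) Define a missed cancer as one diagnosed within a fixed interval after a negative DTS, for example 12 months, with longer intervals as sensitivity analyses. State how cancers found at the next round are counted, report later cancers separately, and give exact confidence intervals. Settle this before results are seen.

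(c) Ask the existing status questions for ineligible and deceased subjects too, use existing hospital records where consent allows, and report the number with unknown status.

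(d) Do not report patient-level sensitivity for the 5-year DTS. Label any ROC analysis as reader-level or as limited to CT-verified subjects.

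The cost is protocol wording, the present questions put to two more groups, and record look-ups, with no extra imaging or readers. The downsides are few events and wide intervals at 12 months, some contact with next of kin, consent limits on record checks, and diagnoses made elsewhere that may be missed.
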